## **7.4 EQ-5D**

The Euro Quality of Life Questionnaire (EQ-5D) will be presented as descriptive summary table by visit. Acceptability of HnB and of EC will be analyzed through the assessment of several questionnaires. The analyses will be presented through the five dimensions (i.e. Mobility, Self-Care, Usual Activities, Pain/Discomfort, Anxiety/Depression) and a Visual Analogue Scale (EQ VAS). Changes from the Baseline Visit to all the subsequent study visits will be also generated. The results will be included in Table E.6 (Appendix 2).

The t-test will be carried out on the differences at final visit to baseline. In case the normality assumption is not verified, the corresponding non parametric test will be adopted. The results will be

	e-CIG VS. IQOS Statistical Analysis Plan Version 2.0	Doc code: BIOSTAT.SAP.02
		Pag. 16 of 115

included in Table E.4a2 (Appendix 2). These data will also be listed (Appendix 3: Listing E.1). The analysis will be presented by all subjects and “Continuous Quitters”.

### 7.5 Step test by visit

The Step test data will be presented as descriptive summary table by visit. The seven items regarding Heart Rate and Oxygen Saturation (i.e. Baseline, Step 1 to 5 and Baseline condition recovery time) will be analysed by HR and SpO2. The two items, (i.e. Stop time and VO2MAX, will be analysed using the same methods (Table E.7a). In details, the latter, is the result of the so called “Chester Step Test” who was computed for each subject at site and reported in the eCRF.

An inferential analysis will be carried out on the changes from baseline by item. The results will be presented in Table E.7b. The data will also be listed (Appendix 3: Listing D.8). The analysis will be presented by all subjects and “Continuous Quitters”.

## 8 STATISTICAL ANALYSES OF SAFETY ENDPOINTS

The Safety will be evaluated on all the subjects in the study through the analysis of the Adverse Events (AEs), i.e. those events, occurred during the study, which could be related or not related with the devices, and the Vital Signs.

No methods for replacing missing values will be applied. The Safety population will be considered for this analysis, therefore all the listings will be built with reference to the full set of enrolled patients. As for the Vital Signs, a further analysis in the subpopulation of the “Continuous Quitter” will be presented.

### 8.1 Extent of Exposure and study duration

The study duration (from Baseline to last Visit) will be summarized in Table S.1 and listed in term of baseline date, final visit date and time interval in days in Listing S.1.

### 8.2 Adverse Events

Adverse Events will be coded using the MedDRA dictionary (last version available). All the events (i.e., all the conditions which started or deteriorated after the Informed Consent signing) observed during the study will be listed (Listing S.2).

The following summary tables (N, %), replied by Group, will be presented:

- ✓ Overview of AEs: number of subjects with any AEs, study product related AEs, serious AEs, study product related serious AEs, AEs leading to withdrawal, AEs leading to death (Table S.2a).

	e-CIG VS. IQOS Statistical Analysis Plan Version 2.0	Doc code: BIOSTAT.SAP.02
		Pag. 17 of 115

- ✓ Incidence of AEs by SOC and PT (Table S.2b).
- ✓ Incidence of serious AEs by SOC and PT (Table S.2c)
- ✓ Incidence of study treatment related AEs (defined as suspected with respect to product relationship in the opinion of the Investigator) by SOC and PT (Table S.2d).
- ✓ Incidence of AEs leading to study withdrawal by SOC and PT (Tables S.2e).
- ✓ Incidence of AEs by severity and by SOC and PT (Table S.2f).

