### Informed Consent

The investigator, or a person designated by the investigator, will explain the benefits and risks of participation in the study to each subject, subject's legally acceptable representative or impartial witness and obtain written informed consent prior to the subject entering the study (before initiation of protocol-specified procedures). The informed consent document must be approved by IRB/IEC and must be in compliance with ICHGCP and in accordance with local regulatory and legal requirements, in language readily understood by the subject. Each subject's original consent form, signed and dated by the subject or by the subject's legally acceptable representative, and a witness to the informed consent discussion, will be retained by the investigator.

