### **Minimum Glossary**

**Efficacy:** the quit rate derived from the use of the product (HnB or EC)

**Adoption rate:** the daily product use (HnB or EC), measured independently from tobacco cigarette consumption

**Tolerability:** the incidence of adverse or serious adverse events derived from the use of the product (HnB or EC)

**Tobacco harm reduction:** reduction of selected biomarkers of exposure in spot urine and improvement in some biological parameters.

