**VISIT SCHEDULE**

	V0 (screening)	Visit 1 (baseline)	Visit 2	Visit 3	Visit 4	Visit 5	Visit 6	Visit 7 Follow-up
Assessment		≤ 7 days after V0	1 week after visit +/-3 days	2 weeks after visit 1 +/-3 days	4 weeks after visit 1 +/-3days	8 weeks after visit 1 +/-7 days	12 weeks after visit 1 +/-7 days	24 weeks after visit 1 +/-7 days
Medical/smoking/vaping/new generation product use history	X							X
Instructions for urine collection and storage; delivery of containers	X			X				
Eligibility criteria verification and confirmation	X							
Informed consent		X						
Vital Signs (BP, HR)		X	X	X	X	X	X	X
Weight and height		X					X	X
Urine sample pick up		X			X			
Randomization		X						
Training for the allocated device (from 30min to 2 hours)		X						
Device delivery (included 1 week supply heatsticks for iQOS or eliquid for JustFog)		X						
Providing 1 week supply of heatsticks for iQOS or eliquid for JustFog			X					
Providing 2 weeks supply of heatsticks for iQOS or eliquid for JustFog				X				
Providing 4 weeks supply of heatsticks for iQOS or eliquid for JustFog					X	X		
Smoking consumption/abstinence/reduction recording through subject self-reporting		X	X	X	X	X	X	X
Device and supply accountability (collection of empty e-liquid refill bottles)			X	X	X	X	X	

and used heathsticks; eventual substitution of malfunctioning devices)								
mCEQ					X	X	X	X
Smoking Cue Appeal (8 items)					X	X	X	X
ITUQ – items 4-6					X	X	X	X
Risk perception (PRI-P CC e PRI- P RRP)					X	X	X	X
EQ-5D		X			X	X	X	X
eCO		X	X	X	X	X	X	X
Step test		X			X		X	X
Safety and product reliability monitoring/reporti ng		X	X	X	X	X	X	X

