**Visit schedule description:**

**V0:** Screening visit for eligibility criteria. Recording of the medical history and smoking behavior of the participant. Selected participants will sign an Informed Consent. Selected participants will be instructed on how to collect and store their first morning urine (containers for urine collection will be delivered to them during the screening) before bringing it to the hospital on the day established for Baseline/Visit 1. (SOPs are available).

**Visit 1 (V1)** (to be programmed within 1 week from V0): Eligibility criteria confirmation, All Baseline assessments, Self-reported daily conventional cigarette consumption recording (baseline measurement), Randomisation, HnB or EC free supply for 1 week and familiarization period to choose the preferred flavor\* (30 min to 2h, as specified below), training on product use, spot urine samples collection and storage.

**Visit 2 (V2):** Week 1 from V1 (with a tolerance of +/- 3 days): vital signs measurement, smoking abstinence/reduction assessment (self-reporting + eCO measurement), adoption rates assessment, HnB or EC free supply for 1 week.

**Visit 3 (V3):** Week 2 from V1 (with a tolerance of +/- 3 days): vital signs measurement, smoking abstinence/reduction assessment, adoption rates assessment, HnB or EC free supply for 2 weeks, repeat instructions for first morning urine collection and storage at V4 and delivery of containers.

**Visit 4 (V4):** Week 4 from V1 (with a tolerance of +/- 3 days): Second hand over of spot urine samples, vital signs measurement, smoking abstinence/reduction assessment, adoption rates assessment, quality of life perception assessment, HnB or EC free supply for 4 weeks, step test, acceptability assessment.

**Visit 5 (V5):** Week 8 from V1 (with a tolerance of +/- 7 days): vital signs measurement, smoking abstinence/reduction assessment, adoption rates assessment, quality of life perception assessment, HnB or EC free supply for 4 weeks, acceptability assessment.

**Visit 6 (V6):** Week 12 from V1 (with a tolerance of +/- 7 days): vital signs and weight/height measurement, smoking abstinence/reduction assessment, adoption rates assessment, quality of life perception assessment, acceptability assessment. End of product free provision.

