**Decisione del Team**

Dopo un'attenta analisi del listato, considerando la tipologia dello studio, il Team ha ritenuto che le piccole differenze rispetto alle finestre di accettabilità osservate in alcune visite non sono da considerare violazioni.

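### Adverse events are counted from informed consent with no cut-off at first product use, so the any-event tables by group can include up to 7 days of pre-product events; the documents also disagree on the consent visit

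*SAP*

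**What the plan says.** **Onset rule.** SAP 8.2 describes the events as "all the conditions which started or deteriorated after the Informed Consent signing". That sentence introduces Listing S.2. Tables S.2a to S.2f follow in the same section with no rule of their own. The SAP defines no treatment-emergent event. The Safety population in SAP section 4 requires at least one use of the product, which selects participants and not events.

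**Scope.** SAP section 8 covers events whether or not they are related to the devices. Product-related events have their own rows in Table S.2a and their own Table S.2d, based on the investigator's causality assessment.

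**Tolerability.** The protocol's Minimum Glossary defines it as "the incidence of adverse or serious adverse events derived from the use of the product (HnB or EC".

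**Timing.** In the protocol's visit description, consent falls under V0: "Selected participants will sign an Informed Consent". The SAP flow chart (Appendix 4) also marks V0. The protocol's schedule table leaves V0 blank in that row and marks Visit 1. V1 is planned "≤ 7 days after V0", and randomisation and first use of the allocated product take place there. The protocol's Informed Consent section says the investigator will "obtain written informed consent prior to the subject entering the study (before initiation of protocol-specified procedures".

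**Exposure.** The footnote to mock Table S.1 counts exposure from the Baseline date.

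**The concern.** An event that starts between consent and first use cannot have been caused by a product the participant has not yet received. If such events enter a table by product group, both arms carry background that has nothing to do with either product, and a difference in tolerability looks slightly smaller than it is. Event counts and exposure also start from different days, consent for one and Baseline for the other.

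Such events have a route into the data. The protocol's safety and tolerability section has adverse events, and symptoms attributed to smoking, recorded at baseline on the adverse event page.

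The conflict over the consent visit matters in its own right. Under the schedule table, history taking and the urine-collection instructions at V0 would come before consent, as would the urine collected for V1. That does not fit the Informed Consent section.

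**Working it through.** The plan states no figure for the pre-product window and no adverse event rate, so there is none to reproduce.

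**1. Consent visit, source by source**

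| Source | Consent at | Planned lead-in before first use |
|---|---|---|
| Protocol, visit description | V0 | 0 to 7 days |
| SAP, Appendix 4 flow chart | V0 | 0 to 7 days |
| Protocol, schedule table | V1 | same day at most |

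The lead-in exists only if consent is at V0. The SAP's own chart says V0, so that reading applies to the SAP analysis.

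**2. Share of the counting window**

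Safety monitoring is marked through V7, nominally 24 weeks = 168 days after V1. For a V0–V1 gap of *d* days, the pre-product share is *d* / (*d* + 168):

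- *d* = 7: 7/175 = 4.0%
- *d* = 3: 3/171 = 1.8%
- *d* = 0: 0%

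These are shares of time, not of events. Seven days is the planned maximum. The Data Review Meeting minute records that "il Team ha ritenuto che le piccole differenze rispetto alle finestre di accettabilità osservate in alcune visite non sono da considerare violazioni" (small departures from the visit windows at some visits were not treated as violations). It does not name the visits, so a somewhat longer gap cannot be ruled out.

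**3. What this could do to a table (assumed rates)**

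Suppose a proportion *p* of participants has at least one event in the 168 days after V1, at a constant rate. With a full 7-day lead-in the proportion becomes 1 − (1 − *p*)^(175/168):

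| Assumed *p* | With lead-in | Extra participants per 110 |
|---|---|---|
| 10% | 10.4% | 0.4 |
| 30% | 31.0% | 1.1 |
| 50% | 51.4% | 1.6 |

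For dilution, assume true risks after first use of 20% and 10%, and a 2% risk before it in both arms:

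- 1 − 0.80 × 0.98 = 21.6%
- 1 − 0.90 × 0.98 = 11.8%

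The difference falls from 10.0 to 9.8 percentage points and the ratio from 2.00 to 1.83.

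**4. Which outputs are exposed**

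- Any-event row of S.2a, S.2b (class and term) and S.2f (severity): exposed, because no onset rule or causality filter applies.
- Related-event rows of S.2a, and S.2d: little affected, because an event before first use should not be judged product-related.
- Serious events, S.2c: unaffected in practice; the minute (its section 2.7) reports none.

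**The case against.** Recording events from consent is normal, and the SAP sentence is literally a rule for a listing. That stands as far as it goes: early events belong in the listing. That the tables use the same window is an inference, but no other rule is offered, so a programmer would apply this one.

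Four stronger readings are tempting, and the documents do not support them.

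- *Tolerability as the protocol defines it includes pre-product events.* The related-event outputs correspond to the glossary definition and filter on causality. The gap is in the broader any-event tables.
- *The conflicting schedule starts the event clock at different points for different participants.* Under the schedule table everyone starts at V1. A lead-in that varies from 0 to 7 days comes from the V0 reading, and nothing shows that participants were handled under different documents.
- *Pooling weeks 12 to 24 is an error because free supply has stopped.* The protocol plans tolerability at 24 weeks, and participants may go on using the product; mock Listing D.11 asks whether they do.
- *The share is 7/91 = 7.7%.* That is the window to week 12, and no adverse event table is planned to stop there.

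It is also fair that events between V0 and V1 may be incompletely captured, since both charts mark safety monitoring from V1. That would shrink the effect further.

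**Conclusion.** The point holds as a minor gap in definition. The any-event, class/term and severity tables by group can include events from before randomisation and exposure, for at most 7 of about 175 days (4%) under the planned visit window. Because these events precede randomisation, they should be balanced between arms in expectation. The result is a slight inflation of both arms and a slight dilution of any difference. A reader should not infer a bias in favour of either product.

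This rests on consent at V0, on the planned 7-day limit, and on the SAP 8.2 onset rule carrying over to the tables. The participant counts in the working also assume an event rate, which the documents do not give.

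The conflict over the consent visit is a separate inconsistency. It stands whatever its effect on event counts.

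**What to change.** 1. In SAP 8.2, count in the summary tables only events that start or worsen on or after first product use at V1. Keep earlier events in Listing S.2, flagged as pre-product.
2. Show the onset date in Listing S.2. The mock listing as it reads here has no clear onset column; its start and end dates appear to belong to hospitalisation, though the header may have been damaged in conversion. Check that the eCRF holds the date. The existing after-consent rule needs it too.
3. Reconcile the consent row of the protocol's schedule table with the visit description, the Informed Consent section and the SAP flow chart.

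The cost is one definition, one date filter, one listing column if it is missing, and one reconciled row, provided the onset date was collected. If the SAP is not reissued, its introduction already provides for explaining deviations in the Statistical Report. Showing V1–V6 and V6–V7 separately would help a reader, but it is optional and corrects no error.

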#### **Safety assessments:**

Descriptive statistics will be used to summarize the number and percentage of subjects experiencing adverse events

and adverse reactions by study group. Parametric and non-parametric data will be expressed as mean ( $\pm$ SD) and median (and interquartile range [IQR]) respectively. Within-group (from baseline) and between-group differences were evaluated by means of parametric and non parametric statistical tests, for paired and unpaired data, as appropriate. Significance of differences in frequency distribution of categorical variables will be tested by  $\chi^2$  test.

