### 2.2 Study Objectives

The primary objective of this study is to compare the efficacy of HnB and EC, in terms of quit rates at week 12, by self-reporting abstinence from classic cigarette [validated by an Exhaled breath Carbon monoxide (eCO) measurement  $\leq 10$ ppm].

The secondary objectives are:

- 1) to compare the smoking reduction derived from the use of HnB and EC, intended as a 50% reduction in the number of conventional cigarette/day at week 12, defined through self-reporting;
- 2) to compare the adoption rate, and adherence to product use [by collecting (empty) refill bottles and used heatsticks on a daily basis, verified by a study diary filled daily by the subject];
- 3) to compare the acceptability of HnB and of EC, through the assessment of product satisfaction, risk perception, effects on craving and nicotine withdrawal, product preferences, subjective and sensorial effects by:
  - a) Modified Cigarette Evaluation Questionnaire (mCEQ) adapted for EC and HnB users;
  - b) three of 8 items of "Smoking Cue Appeal" adapted for EC and HnBusers;
  - c) "Intent to use questionnaire" (ITUQ) – items 4-6;
  - d) PRI-P CC Perceived Health Risk scale (for classic cigarette)
  - e) PRI-P RRP Perceived Health Risk scale (for reduced risk products)
  - f) percentage of choice of a particular subtype of heatstick (HnB) or e-liquid.
- 4) to compare the tolerability of HnB and EC, in terms of: self-reported adverse and serious adverse events by study participants, vital signs (BP, HR and body weight) measurements.
- 5) to compare the tobacco harm reduction between HnB and EC, in terms of:
  - a) changes in Biomarkers of Biological Effects (BoBE) such as: eCO in the exhaled breath (i.e. eCO), step test values;

	
e-CIG VS. IQOS Statistical Analysis Plan Version 2.0
	Doc code: BIOSTAT.SAP.02
		Pag. 8 of 115

b) measurement of 14 selected Biomarkers of Exposure (BoE) in spot urine samples of study participants:

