### 8.3 Vital signs

Each Vital Sign, i.e. Weight, Height (at baseline only), BMI, Body Fat (FatM and FatP) Total Body Water, Fat Free Mass, Bone Body Mass, Metabolic Age, Visceral Fat, PAS, PAD and HR will be summarized by timepoint using descriptive summaries as described in Section 5.

All the variables will be measured across all the study visits. Changes from the Baseline Visit to all the subsequent study visits will be also generated.

Table S.3 will include the summaries of the Vital Signs by group. A listing will be also produced (Listing S.2).

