## SAFETY ENDPOINTS

	e-CIG VS. IQOS Statistical Analysis Plan Version 2.0	Doc code: BIOSTAT.SAP.02
		Pag. 63 of 115

Sponsor: Center for Tobacco Research, Cessation and Prevention, [name]  
Protocol: Progetto e-cig vs IQOS

Table S.1 Summary of Extent of Exposure by group  
Population: Safety

		Group HnB	Group EC
		N=XXX	N=XXX
Extent of Exposure	N	XX	XX
	N missing	XX	XX
	Mean	XX.X	XX.X
	Std. deviation	XX.X	XX.X
	Median	XX.X	XX.X
	Q1-Q3	XX.X - XX.X	XX.X - XX.X

---

<File: [..]\Work\_In\_Progress\[..]\Statistica\Programmi\xxxxx.sas>  
<Source: [..]\Work\_In\_Progress\[..]\Gestione Dati\Dati SAS\xxxxx.sas7bdat>      Generated on XXXXXXXXXX XX:XX  
The Extent of exposure is computed as (Visit 6 date - Baseline date)  
For further information see Listing X.X

	e-CIG VS. IQOS Statistical Analysis Plan Version 2.0	Doc code: BIOSTAT.SAP.02
		Pag. 64 of 115

Sponsor: Center for Tobacco Research, Cessation and Prevention, [name]  
Protocol: Progetto e-cig vs IQOS

Table S.2 Summary of Adverse Drug Reactions by group  
Population: Safety

	Group HnB N=XXX	Group EC N=XXX
ADRs	XX (XX.X%)	XX (XX.X%)
SADRs	XX (XX.X%)	XX (XX.X%)
Related ADRs	XX (XX.X%)	XX (XX.X%)

<File: [..]\Work\_In\_Progress\[..]\Statistica\Programmi\xxxxx.sas>  
<Source: [..]\Work\_In\_Progress\[..]\Gestione Dati\Dati SAS\xxxxx.sas7bdat>

Generated on XXXXXXXXXX XX:XX

The percentages are calculated on the total of the enrolled patients by group  
ADRS classified as Possible/Probably/Definite are considered as Related ADRS  
For further information see Listing X.X

e-CIG VS. IQOS  
Statistical Analysis Plan  
Version 2.0

Doc code:  
BIOSTAT.SAP.02

Pag. 65 of 115

Sponsor: Center for Tobacco Research, Cessation and Prevention, [name]  
Protocol: Progetto e-cig vs IQOS

Table S.3 Summary of Vital Signs by group < Group HnB / Group EC >  
Population: <Safety/Continuous Quitters>

Parameter <Unit>	Visit	Observed Values at Visit							Changes From Visit 1 to Visits 6 and 7						
		N	N miss	Mean	STD	CI 95%	Median	Range (Q1-Q3)	N	N miss	Mean	STD	CI 95%	Median	Range (Q1-Q3)
parameter #1 <um>	Baseline	XX	XX	XX.XX	XX.XX	[XX.XX,XXX.X]	XX.XX	(XX.XX - XXX.X)							
	Visit 2	XX	XX	XX.XX	XX.XX	[XX.XX,XXX.X]	XX.XX	(XX.XX - XXX.X)							
	. . . . . Follow-up	XX	XX	XX.XX	XX.XX	[XX.XX,XXX.X]	XX.XX	(XX.XX - XXX.X)	XX	XX	XX.XX	XX.XX	[XX.XX,XXX.X]	XX.XX	(XX.XX - XXX.X)

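### Comparing tolerability is a secondary objective, but the SAP plans no between-arm difference, interval or test for adverse events or vital signs, and its AE tables do not separate the supplied 12 weeks from follow-up

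*SAP*

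**What the plan says.** **Objective.** SAP 2.2 (item 4) sets out "to compare the tolerability of HnB and EC, in terms of: self-reported adverse and serious adverse events by study participants", together with BP, HR and body weight. The protocol's secondary endpoint 5 says the same. The protocol glossary defines tolerability as the incidence of events arising from use of the product.

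**Protocol analysis.** The Safety assessments paragraph opens with descriptive counts and percentages of subjects with adverse events and reactions. It then says that within-group and "between-group differences were evaluated by means of parametric and non parametric statistical tests, for paired and unpaired data, as appropriate". For categorical data it adds: "Significance of differences in frequency distribution of categorical variables will be tested by" a chi-square test.

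**SAP analysis.** Section 5 describes the protocol's analysis as descriptive. For adverse events, SAP 8.2 says "The following summary tables (N, %), replied by Group, will be presented". Its window is "all the conditions which started or deteriorated after the Informed Consent signing", with no division at week 12. For vital signs, SAP 8.3 lists the variables and ends "PAS, PAD and HR will be summarized by timepoint using descriptive summaries as described in Section 5".

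**Shells.** Table S.2 has one column of counts per arm. Table S.3 gives values by visit and a block headed "Changes From Visit 1 to Visits 6 and 7", with 95% intervals within each arm only.

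**The concern.** A secondary objective worded as a comparison needs at least one quantity that compares the arms. As the SAP stands, a reader gets two percentages for adverse events and two sets of means for vital signs, and has to judge the gap by eye. That is a real loss in a head-to-head trial of two products.

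This is not the SAP's general approach. It names between-group tests for smoking reduction (7.2.1), adherence (7.2.2), the questionnaires (7.2.3 to 7.2.7) and eCO (7.3). Section 5 gives the only apparent reason for treating safety differently, namely that the protocol's analysis is descriptive, and this does not match the Safety assessments paragraph. The data review minutes (section 2.5) record that no change to the SAP was requested, so version 2.0 leaves the gap in place.

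The AE window is a second, smaller problem. Free supply ends at V6 (protocol, Follow-up Visit), yet events from consent to V7 go into one table. A difference that arises during supplied use can be diluted by events in a later period when use is no longer supplied and may vary.

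**Working it through.** **1. Is tolerability sized anywhere?** The only sample-size figure is 104 per group for the quit rate. It reproduces. With both rates 0.25, margin 0.15, one-sided alpha 0.05 and power 0.80, the Farrington-Manning rates constrained under the null are about 0.189 and 0.339.

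- s0 = √(0.189×0.811 + 0.339×0.661) ≈ 0.614
- s1 = √(2×0.25×0.75) ≈ 0.612
- n = [(1.645×0.614 + 0.842×0.612)/0.15]² ≈ 103.5, rounded up to 104

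It has no bearing on tolerability, for which no sizing is given.

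**2. The documents side by side.**

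| Item | Protocol, Safety assessments | SAP 8.2, 8.3 and shells |
|---|---|---|
| AE counts and % by arm | yes | yes |
| Between-group test, categorical | chi-square, general wording | none |
| Between-group test, continuous | parametric or non-parametric, general wording | none |
| Between-arm difference or CI | not mentioned | none |

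**3. What an interval would show.** The inputs are 220 in the Safety population (SAP 9.7). The split is not given, so I assume about 110 per arm from the 1:1 allocation. AE rates are also assumed, because the documents give none. With equal rates p, the half-width is 1.96×√(2p(1−p)/110).

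- p = 0.10: 1.96×√(0.18/110) = 7.9 points
- p = 0.20: 1.96×√(0.32/110) = 10.6 points
- p = 0.30: 1.96×√(0.42/110) = 12.1 points

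The same 10-point gap reads differently according to the base rate:

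- 10% vs 20%: 10 ± 1.96×√((0.09+0.16)/110), or 0.7 to 19.3 points
- 30% vs 40%: 10 ± 1.96×√((0.21+0.24)/110), or −2.5 to 22.5 points

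At 80% power (two-sided 0.05), base rates of 10%, 20% and 30% need about 24%, 37% and 48% in the other arm. The comparison is therefore unpowered for modest differences, which favours estimates with intervals over p-values.

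**4. Effect of one AE window.** Free supply covers 12 of 24 weeks, or 84 of 168 nominal days. As an illustration, take assumed rates of 30% vs 15% up to week 12, then an equal and independent rate c in both arms. The cumulative difference is (1−0.15)(1−c) − (1−0.30)(1−c) = 0.15(1−c).

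| c, weeks 12–24 | Cumulative rates | Difference | Power at 110 per arm |
|---|---|---|---|
| weeks 0–12 only | 30% vs 15% | 15.0 | 76% |
| 10% | 37.0% vs 23.5% | 13.5 | 59% |
| 20% | 44.0% vs 32.0% | 12.0 | 45% |
| 30% | 51.0% vs 40.5% | 10.5 | 34% |

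If the arms also differ after V6, the dilution is smaller or absent.

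**The case against.** Several points on the other side stand and limit the finding.

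- **A comparison of sorts is made.** The arms appear side by side, and an unadjusted difference with its CI can be worked out from the overall counts, or from the means and SDs. It would be wrong to infer that the objective has been abandoned. The tables do not, however, yield a baseline-adjusted difference or a split of events at V6.
- **The protocol wording is loose.** The only sentence in Safety assessments that names adverse events is descriptive, and SAP 8.2 delivers it. The test sentences are general and name neither adverse events nor vital signs. A reader might infer that the protocol prespecified a chi-square test of AE incidence; the text does not go that far. Still, the sentences sit under the safety heading, and Section 5 of the SAP does not account for them.
- **Only the AE tables are pooled.** Vital signs are given by visit, with separate changes to V6 and V7.
- **The end of free supply is not shown to be the end of use.** V7 assesses product usage, and Listing D.11 asks whether participants still use the study product. The 84 days cannot be read as unexposed time. Table S.1 is no firm evidence either: its shell footnote stops exposure at V6, while SAP 8.1 runs from baseline to the last visit.
- **Splitting events may not be straightforward.** Listing S.2 shows no onset date and no visit column, although the protocol has events recorded at each visit.
- **Serious events leave little to compare.** The data review minutes (section 2.7) report none.
- **Baseline adjustment goes beyond the protocol.** It is a recommendation for precision, not something the SAP failed to carry over.

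**Conclusion.** The point holds in a limited form. Tolerability is a stated comparative objective. The protocol allows for between-group safety tests in general terms, and the SAP provides no between-arm difference, interval or test for adverse events or vital signs. Its reason, that the protocol's analysis is descriptive, does not match the protocol's safety paragraph. Separately, the AE tables, and only those, merge the supplied 12 weeks with follow-up to week 24.

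On assumed AE rates of 10% to 30% and an assumed 110 per arm, the unreported uncertainty is about ±8 to ±12 points. These figures do not support a general claim that a 10-point gap cannot be told from noise: the interval excludes zero at 10% vs 20% and includes it at 30% vs 40%. The planned tables do not show which case applies. The dilution figures are illustrative and depend on equal rates after V6.

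The primary result is unaffected. This should be corrected because a stated objective otherwise has no between-arm estimate, but it does not threaten the trial's main conclusion.

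**What to change.** - **SAP 8.2 and shell S.2:** add the HnB minus EC risk difference with 95% CI for any AE and for product-related AE. Show it for events up to V6, for events after V6, and overall. Assign events by onset date if recorded, otherwise by the visit at which they were recorded. Name the interval method.
- **SAP 8.3 and shell S.3:** add the baseline-adjusted HnB minus EC difference with 95% CI at V6 for systolic BP, diastolic BP, HR and body weight. BP and HR are scheduled at every visit from V1, and weight at V1, V6 and V7, so the data are planned. SAP 8 rules out replacing missing safety values, so state the number contributing in each arm.
- **Labelling:** describe these as unpowered estimates.
- **SAP 5:** correct the statement that the protocol's analysis is descriptive. If no between-arm safety analysis is wanted, record that as a departure from the protocol's Safety assessments section and give the reason.

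The cost is some SAP wording, a few extra table columns and a check that AE timing can be recovered from the eCRF. If that check fails, the overall difference with its CI can still be reported.
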